#### 8. BIOSPECIMEN STUDIES AND PROCEDURES

See Correlative Laboratory Manual for collection, processing and shipping instructions for all tissue and blood specimens.

#### 8.1 Correlative Analyses

Tissue based and peripheral-blood based correlative analyses will focus on the identification of biomarkers of response and resistance to treatment with olaparib and will include, but not be limited to, DNA, RNA, and protein-based assays. Because all patients enrolled on this study will have been previously identified as having a DDR mutation, we will obtain prior genetic sequencing reports for exploratory analyses of co-alterations and response/resistance to treatment and time-to-event outcomes. Furthermore, whole exome sequencing may be pursued on select archival specimens, or all specimens, to better define the genomic landscape. Circulating DNA will be utilized to correlate genomic alterations in the peripheral blood with alterations present in tumor tissue.

In addition to the analyses described above, we may generate circulating tumor cell-based patient-derived xenograft models and/or organoids using an approach that we have previously described.  The feasibility of establishing these models will be assessed and if successful, we will evaluate sensitivity and resistance to olaparib in these model systems.

#### 8.2 Archival Tissue

All subjects must have adequate archival tissue available; identified at screening and shipped by C1D1 (i.e., at least 15 unstained slides or paraffin block). Archival tissue should represent invasive or metastatic urothelial cancer with a preference for metastatic tissue if available. If archival tissue is not available, enrollment must be discussed with the sponsor-investigator on a case by case basis.

#### 8.3 Peripheral Blood

All samples to be drawn prior to study drug administration (if applicable). Serial blood samples will be collected to support biomarker research; There are 4 time points for blood samples to be obtained: (1) pre-dose C1D1, (2) pre-dose C3D1, (3) pre-dose C5D1 and at (4) Progression. If a subject comes off study due to progression, samples may be obtained at the Safety Follow Up visit.

# 8.4 Tumor Specimens Obtained at the Time of Disease Progression or for Other Clinical Purposes

Subjects may have tumor tissue obtained during the course of the study or at the time of disease progression for clinical purposes (e.g., confirmation of disease progression, management of complication of disease progression, etc.). Specimens obtained in these settings may be accessed by the research team to facilitate an understanding of the pharmacodynamic effects of treatment at the level of the tumor and microenvironment including mechanisms of treatment resistance.

#### 8.5 Samples for Future Unspecified Cancer Related Research

Subject consent will be obtained for additional samples collected for future unspecified cancer related research. Hoosier Cancer Research Network will manage the banked samples. Samples will be banked indefinitely in the Hoosier Cancer Research Network Biorepository.

Version Date: 15MAY2019 Confidential Page 41 of 60

• Whole Blood will be collected prior to treatment on Cycle 1 Day 1, C3D1, C5D1 and at progression/D30 Safety Follow-up visit.

# 8.6 Storage of Excess Biospecimens

Excess biospecimens not completely utilized in these experiments will be stored indefinitely at HCRN for future use in research focused on GU malignant diseases that are yet to be determined. All specimens collected will maintain the assigned unique study number of the corresponding patient. Deidentified samples may be shared with other research institutions. We believe that allowing for storage and usage of the remaining samples for future research is ethically justified and a preferred option to discarding these materials given the potential impact on improving clinical outcomes for subjects with bladder cancer. Subjects will be given the option to store excess specimens during the informed consent process.

# 8.7 Confidentiality of Biospecimens

Samples that are collected will be identified by a subject's sequence ID number assigned at the time of registration to the trial. Any material issued to collaborating researchers will be anonymized and only identified by the subject's sequence number.

#### 9. CRITERIA FOR DISEASE EVALUATION

#### 9.1 Measurable Disease

Measurable disease is defined as the presence of at least one measurable lesion. Measurable lesions are defined as those that can be accurately measured in at least one dimension (longest diameter to be recorded) as  $\geq 20$  mm by chest x-ray, as  $\geq 10$  mm with CT scan, or  $\geq 10$  mm with calipers by clinical exam. All tumor measurements must be recorded in millimeters (or decimal fractions of centimeters).

#### 9.1.1 Malignant Lymph Nodes

To be considered pathologically enlarged and measurable, a lymph node must be  $\ge 15$  mm in short axis when assessed by CT scan (CT scan slice thickness recommended to be no greater than 5 mm). At baseline and in follow-up, only the short axis will be measured and followed.

### 9.2 Non-measurable Lesions

All other lesions (or sites of disease), including small lesions (longest diameter <10 mm or pathological lymph nodes with  $\geq$  10 to <15 mm short axis), are considered non-measurable disease. Bone lesions, leptomeningeal disease, ascites, pleural/pericardial effusions, lymphangitis cutis/pulmonitis, inflammatory breast disease, and abdominal masses (not followed by CT or MRI), are considered as non-measurable.

**NOTE:** Cystic lesions that meet the criteria for radiographically defined simple cysts should not be considered as malignant lesions (neither measurable nor non-measurable) since they are, by definition, simple cysts. 'Cystic lesions' thought to represent cystic metastases can be considered as measurable lesions, if they meet the definition of measurability described above. However, if non-cystic lesions are present in the same subject, these are preferred for selection as target lesions.

Version Date: 15MAY2019 Confidential Page 42 of 60

# 9.3 Target Lesions

All measurable lesions up to a maximum of 2 lesions per organ and 5 lesions in total, representative of all involved organs, should be identified as target lesions and recorded and measured at baseline. Target lesions should be selected on the basis of their size (lesions with the longest diameter), be representative of all involved organs, but in addition should be those that lend themselves to reproducible repeated measurements. It may be the case that, on occasion, the largest lesion does not lend itself to reproducible measurement in which circumstance the next largest lesion which can be measured reproducibly should be selected. A sum of the diameters (longest for non-nodal lesions, short axis for nodal lesions) for all target lesions will be calculated and reported as the baseline sum diameters. If lymph nodes are to be included in the sum, then only the short axis is added into the sum. The baseline sum diameters will be used as reference to further characterize any objective tumor regression in the measurable dimension of the disease.

# 9.4 Non-target Lesions

All other lesions (or sites of disease) including any measurable lesions over and above the 5 target lesions should be identified as non-target lesions and should also be recorded at baseline. Measurements of these lesions are not required, but the presence, absence, or in rare cases unequivocal progression of each should be noted throughout follow-up.

# 9.5 Evaluation of Target Lesions

**NOTE:** In addition to the information below, also see the international criteria proposed by the Response Evaluation Criteria in Solid Tumors (RECIST) Committee, version 1.1 (Eur J Cancer 45;2009:228-247) for special notes on the assessment of target lesions.

Complete Response (CR)	Disappearance of all target lesions. Any pathological lymph nodes (whether target or non-target) must have reduction in short axis to <10 mm.
Partial Response (PR)	At least a 30% decrease in the sum of the diameters of target lesions, taking as reference the baseline sum diameters
Progressive Disease (PD)	At least a 20% increase in the sum of the diameters of target lesions, taking as reference the smallest sum on study (this includes the baseline sum if that is the smallest on study). In addition to the relative increase of 20%, the sum must also demonstrate an absolute increase of at least 5 mm. (Note: the appearance of one or more new lesions is also considered progressions).
Stable Disease (SD)	Neither sufficient shrinkage to qualify for PR nor sufficient increase to qualify for PD, taking as reference the smallest sum diameters while on study

Version Date: 15MAY2019 Confidential Page 43 of 60

9.6 Evaluation of Non-Target Lesions

	Disappearance of all non-target lesions and normalization of tumor marker level. All lymph nodes must be non-pathological in size (<10 mm short axis)
Complete Response (CR)	
	NOTE: If tumor markers are initially above the upper normal
	limit, they must normalize for a subject to be considered in
	complete clinical response.
Non-CR/ Non-PD	Persistence of one or more non-target lesion(s) and/or maintenance
Non-CR/ Non-FD	of tumor marker level above the normal limits
	Appearance of one or more new lesions and/or unequivocal
	progression of existing non-target lesions. Unequivocal progression
Progressive Disease (PD)	should not normally trump target lesion status. It must be
	representative of overall disease status change, not a single lesion
	increase.

Although a clear progression of "non-target" lesions only is exceptional, the opinion of the site investigator should prevail in such circumstances, and the progression status should be confirmed at a later time by the sponsor investigator.

# 9.7 Evaluation of Best Overall Response

Target Lesions	Non-Target Lesions	New Lesions	Overall Response
CR	CR	No	CR
CR	Non-CR/ Non-PD	No	PR
CR	Not evaluated	No	PR
PR	Non-PD/ or not all evaluated	No	PR
SD	Non-PD or not all evaluated	No	SD
Not all evaluated	Non-PD	No	Non-evaluable
PD	Any	Yes or No	PD
Any	PD*	Yes or No	PD
Any	Any	Yes	PD
*In exceptional circumstances unequivocal progression in non-target lesions may be			

\*In exceptional circumstances, unequivocal progression in non-target lesions may be accepted as disease progression.

Subjects with a global deterioration of health status requiring discontinuation of treatment without objective evidence of disease progression at that time should be classified as having "symptomatic deterioration." Every effort should be made to document the objective progression even after discontinuation of treatment.

In some circumstances, it may be difficult to distinguish residual disease from normal tissue. When the evaluation of complete response depends on this determination, it is recommended that the residual lesion be investigated (fine needle aspirate/biopsy) to confirm the complete response status.

Version Date: 15MAY2019 Confidential Page 44 of 60

# 9.8 Definitions for Response Evaluation – RECIST 1.1

# 9.8.1 First Documentation of Response

The time between initiation of therapy and first documentation of PR or CR.

# 9.8.2 Confirmation of Response

To be assigned a status of complete or partial response, changes in tumor measurements must be confirmed by repeat assessments performed no less than four weeks after the criteria for response are first met.

# 9.8.3 **Duration of Response**

Duration of overall response—the period measured from the time that measurement criteria are met for complete or partial response (whichever status is recorded first) until the date that recurrent or progressive disease is objectively documented (taking as reference for progressive disease the smallest measurements recorded since treatment started).

# 9.8.4 Duration of Overall Complete Response

The period measured from the time that measurement criteria are met for complete response until the first date that recurrent disease is objectively documented.

# 9.8.5 Objective Response Rate

The objective response rate is the proportion of all subjects with confirmed PR or CR according to RECIST 1.1, from the start of treatment until disease progression/recurrence (taking as reference for progressive disease the smallest measurements recorded since the start of treatment).

#### 9.8.6 Disease Control Rate

The disease control rate is the proportion of all subjects with stable disease (SD) for 8 weeks, or partial response (PR), or complete response (CR) according to RECIST 1.1, from the start of treatment until disease progression/recurrence (taking as reference for progressive disease the smallest measurements recorded since the start of treatment).

# 9.8.7 Time to Progression:

A measurement from the date of initiation of therapy until the criteria for disease progression is met as defined by RECIST 1.1. Subjects who have not progressed or have died due to any cause will be right-censored at the date of the last disease evaluation or date of death.

### 9.8.8 Progression Free Survival

A measurement from the date of initiation of therapy until the criteria for disease progression is met as defined by RECIST 1.1 or death occurs. Subjects who have not progressed will be right-censored at the date of the last disease evaluation.

#### 9.8.9 Overall Survival

Overall survival is defined by the date of enrollment to date of death from any cause.

Version Date: 15MAY2019 Confidential Page 45 of 60

#### 10 DRUG INFORMATION

Please refer to the current version of the Investigator's Brochure (IB) for additional information regarding this drug.

### 10.1 Olaparib

Olaparib (AZD2281, KU-0059436) is a potent PARP inhibitor (PARP-1, -2 and -3).

# 10.1.1 Supplier/How Supplied

Astra Zeneca will supply olaparib at no charge to subjects participating in this clinical trial.

The site investigator shall take responsibility for and shall take all steps to maintain appropriate records and ensure appropriate supply, storage, handling, distribution, and usage of investigational product in accordance with the protocol and any applicable laws and regulations.

The AstraZeneca Pharmaceutical Development R&D Supply Chain will supply olaparib to the investigator as round or oval *film coated tablets*. **NOTE:** The capsule and tablet forms of olaparib should not be substituted as they have different bioavailability and dosing instructions.

Investigational product	Dosage form and strength
Olaparib	100 mg tablet
Olaparib	150 mg tablet

a Descriptive information for olaparib can be found in the Investigator's Brochure

# **10.1.2 Preparation**

When possible, refer to the prescribing information and/or investigator's brochure for details on the preparation of the drug. Dosing and administration should be addressed in the Treatment Plan section.

# 10.1.3 Storage and Stability

All study drugs should be kept in a secure place under appropriate storage conditions. Olaparib tablets should be stored at 20°C to 25°C (68°F to 77°F); excursions permitted to 15°C to 30°C (59°F to 86°F). Protect from moisture.

#### **10.1.4** Handling and Disposal

Investigational drug should be disposed as per institutional policy.

#### 10.1.5 Dispensing

Olaparib must be dispensed only from official study sites and to eligible subjects under the supervision of the site investigator. Olaparib should be stored in a secure area according to local regulations. It is the responsibility of the site investigator to ensure that study drug is only dispensed to subjects.

Labels will be prepared in accordance with Good Manufacturing Practice (GMP) and local regulatory guidelines. The labels will fulfill GMP Annex 13 requirements for labelling. Label text will be translated into local language.

Version Date: 15MAY2019 Confidential Page 47 of 60

Each bottle of olaparib will have an investigational product label permanently affixed to the outside stating that the material is for clinical trial/investigational use only and should be kept out of reach of children. The label will include the dosing instructions and a space for the enrolment code (E-code) to be completed at the time of dispensing.

The label will include the following information:

blank lines for quantity of tablets to be taken enrolment code (E-code)

date of dispensing

Instructions stating that the olaparib tablets should be taken at approximately the same time each morning and evening

#### **10.1.6 Potential Adverse Events**

See the most current IB or package insert for a comprehensive list of adverse events.

#### 11 ADVERSE EVENTS

The descriptions and grading scales found in the NCI CTCAE v4 will be utilized for AE assessment. A copy of the CTCAE v4 can be downloaded from the CTEP website at http://ctep.cancer.gov. All forms for AE/SAE recording and reporting can be found in the Study Procedure Manual or in the EDC system (Documents and Information Tab).

# 11.1 Definitions

#### 11.1.1 Adverse Event (AE)

An AE is any untoward medical occurrence whether or not considered related to the study drug that appears to change in intensity during the course of the study. The following are examples of AEs:

- Unintended or unfavorable sign or symptom
- A disease temporally associated with participation in the protocol
- An intercurrent illness or injury that impairs the well-being of the subject

Abnormal laboratory values or diagnostic test results constitute AEs only if they induce clinical signs or symptoms or require treatment or further diagnostic tests

Hospitalization for elective surgery or routine clinical procedures that are not the result of an AE (e.g., surgical insertion of central line) should not be recorded as an AE.

Disease progression should not be recorded as an AE, unless it is attributable to the study regimen by the site investigator.

Version Date: 15MAY2019 Confidential Page 48 of 60

# 11.1.2 Serious Adverse Event (SAE)

A SAE is an adverse event that:

- Results in death. **NOTE:** Death due to disease progression should not be reported as a SAE, unless it is attributable by the site investigator to the study drug(s)
- Is life-threatening (defined as an event in which the subject was at risk of death at the time of the event; it does not refer to an event which hypothetically might have caused death if it were more severe)
- Requires inpatient hospitalization for >24 hours or prolongation of existing hospitalization. **NOTE:** Hospitalization for anticipated or protocol specified procedures such as administration of chemotherapy, central line insertion, metastasis interventional therapy, resection of primary tumor, or elective surgery, will not be considered serious adverse events.
- Results in persistent or significant disability/incapacity
- Is a congenital anomaly or birth defect
- Is an important medical event (defined as a medical event(s) that may not be immediately life-threatening or result in death or hospitalization but, based upon appropriate medical and scientific judgment, may jeopardize the subject or may require intervention (e.g., medical, surgical) to prevent one of the other serious outcomes listed in the definition above). Examples of such events include, but are not limited to, intensive treatment in an emergency room or at home for allergic bronchospasm; blood dyscrasias or convulsions not resulting in hospitalization; or the development of drug dependency or drug abuse.

# 11.1.3 Olaparib Adverse Events of Special Interest (AESI)

Adverse events of special interest [AESI] are events of scientific and medical interest specific to the further understanding of olaparib's safety profile and require close monitoring and rapid communication by the local investigator to the sponsor-investigator via HCRN. An AESI may be serious or non-serious. Adverse Events of Special Interest for olaparib are the Important Potential Risks of MDS/AML, new primary malignancy (other than MDS/AML) and pneumonitis.

ANY event of MDS/AML, new primary malignancy, or pneumonitis should be reported to AstraZeneca Patient Safety whether it is considered a non-serious AE [eg non-melanoma skin cancer] or SAE, and regardless of site investigator's assessment of causality.

A questionnaire will be sent to any investigator reporting an AESI, as an aid to provide further detailed information on the event. During the study there may be other events identified as AESIs that require the use of a questionnaire to help characterize the event and gain a better understanding regarding the relationship between the event and study treatment.

#### 11.1.4 Overdose of Olaparib

There is currently no specific treatment in the event of overdose with olaparib and possible symptoms of overdose are not established.

Olaparib must only be used in accordance with the dosing recommendations in this protocol. Any dose or frequency of dosing that exceeds the dosing regimen specified in this protocol

Version Date: 15MAY2019 Confidential Page 49 of 60

should be reported as an overdose. Adverse reactions associated with overdose should be treated symptomatically and should be managed appropriately.

An overdose with associated AEs is recorded as the AE diagnosis/symptoms on the relevant AE modules in the eCRF and on the Overdose CRF module. An overdose without associated symptoms is only reported on the Overdose CRF module.

If an overdose on an AstraZeneca study drug occurs in the course of the study, site investigators or other site personnel inform appropriate Hoosier Cancer Research Network (HCRN) within one business day and HCRN will report to AstraZeneca within one business day.

# 11.1.5 Reproductive Reporting Information

# **11.1.5.1 Pregnancy**

All outcomes of pregnancy should be reported to HCRN who will then report to AstraZeneca.

#### 11.1.5.2 Maternal Exposure

If a patient becomes pregnant during the course of the study, olaparib should be discontinued immediately. The outcome of any conception occurring from the date of the first dose until 1 month *after the last dose* should be followed up and documented. Pregnancy itself is not regarded as an adverse event unless there is a suspicion that the investigational product under study may have interfered with the effectiveness of a contraceptive medication. Congenital abnormalities/birth defects and spontaneous miscarriages should be reported and handled as SAEs. Elective abortions without complications should not be handled as AEs. The outcome of all pregnancies (spontaneous miscarriage, elective termination, ectopic pregnancy, normal birth or congenital abnormality) should be followed up and documented even if the patient was withdrawn from the study.

If any pregnancy occurs in the course of the study, site investigators or other site personnel must inform HCRN within one business day and HCRN will report to AstraZeneca within one business day.

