- 13. Females of childbearing potential must be willing to abstain from heterosexual activity or to use 2 forms of highly effective methods of contraception from the time of informed consent until 90 days after treatment discontinuation. The two contraception methods can be comprised of two barrier methods, or a barrier method plus a hormonal method. Males must be willing to abstain from heterosexual activity or to use 2 forms of highly effective methods

Version Date: 15MAY2019 Confidential Page 26 of 60

of contraception from the time of informed consent until 90 days after treatment discontinuation.

Acceptable non-hormonal birth control methods:

- Total sexual abstinence ie, refrain from any form of sexual intercourse in line with the patients' usual and/or preferred lifestyle. Periodic abstinence (eg, calendar ovulation, symptothermal, post-ovulation methods) and withdrawal are not acceptable methods of contraception.
- Vasectomised sexual partner PLUS male condom. With participant assurance that partner received post-vasectomy confirmation of azoospermia.
- Tubal occlusion PLUS male condom
- Intrauterine Device PLUS male condom. Provided coils are copper-banded.

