# 5.2.1.4 Contraception

# Olaparib is regarded as a compound with medium/high fetal risk.

Women of childbearing potential and their partners, who are sexually active, must agree to the use of TWO highly effective forms of contraception in combination [as listed below], throughout the period of taking study treatment and for at least 90 days after last dose of study drug(s), or they must totally/truly abstain from any form of sexual intercourse (see below).

Male subjects and their partners, who are sexually active and of childbearing potential, must agree to the use of TWO highly effective forms of contraception in combination [as listed below], throughout the period of taking study treatment and for 90 days after last dose of study drug(s) due to the unknown effects of the study drug on the sperm, or they must totally/truly abstain from any form of sexual intercourse (see below). Male subjects should not donate sperm throughout the period of taking study treatment and for 90 days following the last dose of study drug(s).

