#### 11.1.5.3 Paternal Exposure

Male subjects should refrain from fathering a child or donating sperm during the study and for 3 months following the last dose. Pregnancy of the patient's partners is not considered to be an adverse event. However, the outcome of all pregnancies (spontaneous miscarriage, elective termination, ectopic pregnancy, normal birth or congenital abnormality) should if possible be followed up and documented. The outcome of any conception occurring from the date of the first dose until 3 months *after the last dose* should be followed up and documented.

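### Dated follow-up of conceptions in female subjects stops 1 month after the last dose, about 60 days before their required contraception ends

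*Combined protocol and SAP*

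**What the plan says.** Section 11.1.5.2 (Maternal Exposure) sets the dated rule for female subjects: "The outcome of any conception occurring from the date of the first dose until 1 month" after the last dose is to be followed up and documented. No other part of the protocol dates this window for women.

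The same section also has two statements without a date. Outcomes of all pregnancies "should be followed up and documented even if the patient was withdrawn from the study", and "If any pregnancy occurs in the course of the study, site investigators or other site personnel must inform HCRN within one business day". Section 11.1.5.1 adds: "All outcomes of pregnancy should be reported to HCRN who will then report to AstraZeneca".

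Women's contraception runs longer. Inclusion criterion 13 in Section 3.1 requires two "methods of contraception from the time of informed consent until 90 days after treatment discontinuation". Section 5.2.1.4 repeats the 90 days after the last dose, as a minimum, and classes olaparib as a medium to high fetal risk.

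For men, Section 5.2.1.4 also sets 90 days of contraception. Section 11.1.5.3 (Paternal Exposure) says "Male subjects should refrain from fathering a child or donating sperm during the study and for 3 months following the last dose", and its dated rule is "The outcome of any conception occurring from the date of the first dose until 3 months" after the last dose.

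**The concern.** The dated window for following conceptions would be expected to cover at least the period in which the protocol still tells subjects to avoid conceiving. It does so for male subjects' partners. For women, who are themselves exposed to the drug, it stops about two months early, and the documents give no reason.

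The rule can apply in this trial. Inclusion criterion 12 admits women of childbearing potential with a negative pregnancy test, and Section 5.2.2.2 warns that olaparib may make hormonal contraceptives less effective.

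At stake is the documentation of a fetal-exposure outcome. A site working from the dated sentence could decide that a conception on roughly days 31 to 90 after the last dose needs no outcome follow-up. The efficacy and safety analyses in Section 12 are not involved.

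**Working it through.** **Inputs**

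| Item | Value | Source |
|---|---|---|
| Dated window, conceptions in female subjects | 1 month after last dose | 11.1.5.2 |
| Women's contraception | 90 days after stopping treatment | 3.1, criterion 13; 5.2.1.4 |
| Dated window, conceptions by male subjects' partners | 3 months after last dose | 11.1.5.3 |
| Men's contraception | 90 days after last dose | 5.2.1.4 |

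A calendar month is 28 to 31 days, and three calendar months are 89 to 92 days.

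**Women: contraception period minus follow-up window**
- Shortest gap: 90 − 31 = 59 days, and 59/90 = 66% of the contraception period.
- Longest gap: 90 − 28 = 62 days, and 62/90 = 69%.
- Taking every possible last-dose date from 2018 to 2021, the gap ranges from 59 to 62 days, with a mean of 59.6.

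**Men: follow-up window minus contraception period**
- 89 − 90 = −1 day to 92 − 90 = +2 days, so the two periods agree.

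**Paternal window minus maternal window**
- 3 months − 1 month = 2 months. Over the same dates this is 59 to 62 days, with a mean of 60.9.

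**Expected conceptions in the gap**

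The documents give neither the number of women of childbearing potential nor a conception rate. Assume 0 to 5 such women among the maximum of 30 subjects (Section 12.3) and a risk of at most 1% per month.
- Lower end: 0 × 2 months × 0.01 = 0.
- Upper end: 5 × 2 months × 0.01 = 0.10.

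**Do the undated sentences close the gap?**

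Survival follow-up continues every 3 months for 2 years (Section 7, footnote 14), so days 31 to 90 would ordinarily fall within the course of the study, although that phrase is not defined. Read broadly, the undated sentences cover those days. Section 11.1.5.3, however, has equally undated wording about all pregnancies and still states a dated window that matches the contraception period. The dated sentence is therefore where the protocol puts the relevant period, and only the maternal figure is short.

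**The case against.** The strongest reply is that the section already deals with the matter. It asks for the outcome of all pregnancies, even after withdrawal, and Section 11.1.5.1 has no time limit, so the 1-month sentence can be read as a minimum duty. That is a fair reading. It means the undated wording probably picks up many conceptions on days 31 to 90, and it rules out calling this a contradiction or a proven gap. It does not make 1 month the right figure for the one sentence that gives a limit.

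Three other arguments have some weight.
- Nothing in the protocol says that the contraception and follow-up periods must be equal, and the men's 90 days has its own stated reason, the unknown effect on sperm. The comparison with women's own 90 days is therefore the stronger of the two.
- One month resembles the 30-day adverse event and SAE windows (Sections 11.2.1 and 11.2.2.1). The documents do not give this as the reason. Those windows also do not prevent a longer one, because outcomes of conceptions within the existing 1-month window will already fall after day 30.
- A longer window does not help detect pregnancies. Testing is scheduled only at screening and before Cycle 1 Day 1, and survival follow-up may be a phone call. This stands: the edit settles what a site does with a conception it learns of, and does nothing to find more of them.

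**Conclusion.** The concern holds as a minor point. The dated maternal window is 59 to 62 days shorter than women's 90-day contraception period, which is 66% to 69% of that period, and about 2 months shorter than the paternal window. The gap depends only on the protocol's own figures and the length of a calendar month.

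The practical effect is very small: 0 to about 0.1 expected conceptions under the two assumptions above, and some of those would be captured by the undated wording. What remains is a figure out of line with the protocol's own precaution, which a site could use to leave an outcome undocumented. The primary endpoint, sample size, stopping rules and all analyses are unaffected.

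**What to change.** In Section 11.1.5.2, change the end of the conception window from 1 month to 90 days after the last dose. This matches women's contraception in Sections 3.1 and 5.2.1.4 and agrees to within a day or two with the 3 months in Section 11.1.5.3. No other text has to change for these periods to agree.

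The cost is one phrase in the protocol and slightly longer pregnancy follow-up for very few subjects.
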